## Cohort E: Patients with mTNBC

- g) Prior PD-1/L1 inhibitor therapy allowed;
- h) Patients must have received treatment for metastatic disease (at least 1 regimen of cytotoxic chemotherapy for metastatic disease);

Participants are eligible to be included in the study only if **all** of the following criteria apply:

8. Must be able to provide informed consent, as described in Appendix 1, which includes compliance with the requirements and restrictions listed in the informed consent form (ICF) and in this protocol, according to local regulations and are at least 18 years of age.
9. Men with partners of childbearing potential must use a condom during intercourse. Men with partners of childbearing potential or women with childbearing potential must agree to use 2 effective methods of contraception including a highly effective contraceptive method of birth control (Appendix 3) during study treatment and for at least 120 days following the last dose of LY3475070 and pembrolizumab or country requirements, whichever is longer. For patients receiving LY3475070 only, contraception should be maintained for 7 days following the last dose. Additional guidance for contraception during and after study intervention are located in Appendix 3.
10. Women of childbearing potential must have a negative urine pregnancy test at the screening visit followed by a negative serum pregnancy test documented within 24 hours prior to initiation of treatment. If the screening urine test is positive or cannot be confirmed as negative, a serum pregnancy test will be required. Additional guidance for pregnancy testing during and after study intervention is located in Appendix 2 and Appendix 3.
11. Have at least 1 measurable lesion using standard techniques by RECIST version 1.1 (Eisenhauer et al. 2009). **Exception:** patients enrolled in the dose escalation phase and mCRPC patients enrolled in Cohort D1 and D2 are **not** required to have measurable disease.
12. Have a performance status (PS) of 0 or 1 on the Eastern Cooperative Oncology Group (ECOG) scale (Oken et al. 1982).
13. Previous treatments: Have discontinued all previous treatments for cancer and recovered from the acute effects of therapy (except alopecia). Patients must have discontinued from previous treatments, as shown below:

Previous Treatment	Length of Time Prior to First Dose of LY3475070
Endocrine therapies	$\geq 14$ days

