### **7.1. Discontinuation of Study Intervention**

Discontinuation of study treatment does not represent withdrawal from the study.

Participants may discontinue study treatment at any time for any reason or be discontinued from the study treatment at the discretion of the investigator should any untoward effect occur. In addition, a subject may be withdrawn by the investigator or the sponsor if enrollment into the trial is inappropriate, the trial plan is violated or for administrative and/or other safety reasons.

A subject must be discontinued from the trial for the following reasons:

- the participant or the participant's designee, for example, parents or legal guardian requests to discontinue investigational product.
- the subject is lost to follow -up

A subject must be discontinued from trial treatment but continue to be followed for any of the following reasons:

- the patient becomes pregnant during the study
- the patient is significantly noncompliant with study procedures and/or treatment
- disease progression. Disease progression should be confirmed per iRECIST 4 to 8 weeks after site-assessed first radiologic evidence of PD in clinically stable participants. Participants, who have unconfirmed disease progression may continue on treatment at the discretion of the investigator until progression per iRECIST. Any participant deemed clinically unstable should be discontinued from study treatment at first radiologic evidence of PD and is not required to have repeat tumor imaging for confirmation of PD by iRECIST.
- unacceptable toxicity
- the patient, for any reason, requires treatment with another therapeutic agent that has been demonstrated to be effective for treatment of the study indication. Discontinuation from study invention will occur prior to introduction of the new agent.
- Recurrent Grade 2 pneumonitis
- Discontinuation of treatment may be considered for participants who have attained a confirmed complete response (CR) and have been treated for at least 8 cycles (at least 24 weeks), receiving [for monotherapy: at least 2 doses of pembrolizumab; for

combination treatment: 2 cycles of the combination including 2 doses of pembrolizumab and at least 75% of the planned doses of LY3475070] beyond the date when the initial CR was declared.

- Pembrolizumab will be discontinued after completion of approximately 2 years of treatment with pembrolizumab (completion of 35 treatments with pembrolizumab).  

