### 8.1.3. Efficacy Assessment for mCRPC Patients

For mCRPC patients enrolled in this trial (both during dose escalation, Cohorts A and B, and dose expansion Cohorts D1 and D2), response criteria set forth by the Prostate Cancer Clinical Trials Working Group 3 will be utilized (Scher et al. 2016). Efficacy will be evaluated on a combination of RECIST v.1.1 (if patient has measurable disease), prostate-specific antigen (PSA) measurements, and bone scintigraphy using  $^{99m}\text{Tc}$ -methylene diphosphonate radionucleotide ( $^{99m}\text{Tc}$  MDP). Multi-parametric MRI may also be used to evaluate response or progression in bone-only disease. Central measurement of circulating tumor cells is planned at a frequency of every 3 weeks but will not be required for efficacy evaluation.

For patients with measurable disease, RECIST v1.1, as described above in Section 8.1.1, will be utilized with the following caveats:

- I. For nodal lesions, separate pelvic vs extra-pelvic disease and record up to 5 nodal lesions in total.
- II. In order to classify as progression, previously normal lymph nodes (<1 cm) must have grown by at least 0.5 cm in the short axis from baseline scan or nadir and be  $\geq 1$  cm in the short axis.
- III. Nodes that have progressed to  $\geq 1.5$  cm in the short axis are considered measurable; nodes that have progressed to 1 cm to <1.5 cm are considered pathologic but subject to clinical discretion and non-measurable.
- IV. Visceral disease should be designated separately as lung, liver, adrenal, or CNS.

All mCRPC patients will undergo a  $^{99m}\text{Tc}$  MDP scintigraphy at baseline to evaluate skeletal disease involvement. Bone lesions should be evaluated every 9 weeks ( $\pm 7$  days) and can be scheduled around CT/MRI disease staging. Due to possible bone flare that can be part of bone healing in response to treatment, and not actual progression, a 2+2 rule should be used for assessment. Progression should only be called if at least 2 new lesions are seen on the first on-treatment scan, followed by at least 2 additional lesions on the second or subsequent post-treatment scans.

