For patients with non-measurable disease, PSA evaluations will be utilized for response assessment to treatment. Prostate-specific antigen will be measured at each treatment cycle (every 3 weeks), but because favorable PSA response to treatment may be delayed, early PSA rises should be ignored until 12 weeks unless patient is rapidly progressing (new lesions on image assessment) with clinical deterioration. After the first evaluation at 12 weeks, PSA response should be evaluated at every 9 weeks for progression. A PSA increase of  $\geq 25\%$  and  $\geq 2$  ng/dL from baseline/nadir, confirmed with a second measurement at least 3 weeks apart, will be considered progression. A PSA decrease from baseline that is  $\geq 50\%$  will be considered a response and should be confirmed with a repeat measurement at least 3 weeks apart.

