**Tumor markers -local laboratory**

PSA	CA-125
CEA	CA 19-9

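### As written, the 2 ng/dL limb of the PSA progression rule is inactive at any reference PSA of 0.08 ng/mL or more, so the rule reduces to a confirmed 25% rise

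*Protocol*

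**What the plan says.** Protocol Section 8.1.3 covers mCRPC patients in dose escalation and in Cohorts D1 and D2. It says that "response criteria set forth by the Prostate Cancer Clinical Trials Working Group 3 will be utilized", but does not reproduce the thresholds in those criteria. It then gives its own PSA rule:

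- Scope: "For patients with non-measurable disease, PSA evaluations will be utilized for response assessment to treatment".
- Progression: a rise of at least 25% and at least 2 "ng/dL from baseline/nadir, confirmed with a second measurement at least 3 weeks apart, will be considered progression".
- Early guard: "early PSA rises should be ignored until 12 weeks unless patient is rapidly progressing", where rapid progression means new lesions on imaging together with clinical deterioration.
- Response: a fall of at least 50% from baseline, to be confirmed by a repeat measurement at least 3 weeks apart.

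The patients concerned are admitted by criterion 11 in Section 5.1, which says that "mCRPC patients enrolled in Cohort D1 and D2 are" excused from having a measurable lesion, as are patients in dose escalation. Cohort D may enrol up to 50 patients (Section 1.1). The Schedule of Activities repeats that PSA is evaluated for progression every 9 weeks after the 12-week evaluation.

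PSA is listed in Appendix 2 under "Tumor markers -local laboratory", with no reporting unit. Neither document gives a minimum PSA for entry or any PSA distribution. SAP Version 1 is based on protocol version (a) and contains no PSA rule.

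**The concern.** A progression rule that joins a relative and an absolute limb normally uses the absolute limb to prevent a small change from a low starting value being called progression on its percentage alone. In the unit stated, the absolute limb is so small that it provides this protection only at very low PSA levels.

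For patients without measurable disease, PSA is the measure that Section 8.1.3 names for assessing response. The section says that meeting the rule is progression, and Section 7.1 lists disease progression among the reasons to stop study treatment. The threshold should therefore mean what its authors intended.

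There is also a risk of uneven application. PSA is measured locally in a multicenter global study, and no reporting unit is given. One site could convert 2 ng/dL literally, while another could apply the number 2 in the unit its laboratory reports. If that unit were ng/mL, the two sites' absolute limbs would differ 100-fold.

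**Working it through.** No sample size, power or error rate depends on this rule, so the plan has no derived figure to reproduce. The check is a unit conversion followed by a comparison of the two limbs.

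**Inputs (Protocol Section 8.1.3).** Relative limb: 25%. Absolute limb: T = 2 ng/dL. The limbs are joined by *and*. R denotes the reference PSA (baseline or nadir).

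**Step 1, conversion.** 1 dL = 100 mL, so T = 2/100 = 0.02 ng/mL.

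**Step 2, smallest rise that qualifies.** Both limbs must be met, so the minimum rise is max(0.25 × R, T).

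**Step 3, where the absolute limb binds.** It binds only if 0.25 × R < T, that is R < T/0.25 = 0.02/0.25 = 0.08 ng/mL. At R = 0.08 a 25% rise is exactly 0.02 ng/mL and already qualifies.

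**Step 4, comparison with a larger limb.** The last column sets T = 2 ng/mL. This is an assumption used only to show sensitivity to the unit. That limb would bind below 2/0.25 = 8 ng/mL.

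| R (ng/mL) | Minimum rise as written (ng/mL) | As % of R | Minimum rise if T = 2 ng/mL (assumed) | As % of R |
|---|---|---|---|---|
| 0.05 | 0.02 | 40% | 2 | 4000% |
| 0.08 | 0.02 | 25% | 2 | 2500% |
| 0.5 | 0.125 | 25% | 2 | 400% |
| 1 | 0.25 | 25% | 2 | 200% |
| 4 | 1 | 25% | 2 | 50% |
| 8 | 2 | 25% | 2 | 25% |
| 20 | 5 | 25% | 5 | 25% |
| 100 | 25 | 25% | 25 | 25% |

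**Step 5, direction.** Any PSA rise that meets the rule with the larger limb also meets it with the smaller one. For the same series of measurements, the written rule therefore calls progression at the same time or earlier, never later. Illustration with assumed values: baseline 4, nadir 1 ng/mL. As written, a confirmed 1.25 ng/mL is progression, although it is still (4 − 1.25)/4 = 69% below baseline. With T = 2 ng/mL, progression would need 1 + 2 = 3 ng/mL.

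**Step 6, share of patients (assumed distribution).** Suppose R is lognormal with median m between 2 and 50 ng/mL and log-SD s between 1 and 2. The share below a cut-off c is Φ((ln c − ln m)/s).

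- Below 0.08 ng/mL, where the written limb still acts: from 0% to 5.4% (highest at m = 2, s = 2).
- Below 8 ng/mL, where a 2 ng/mL limb would have acted: from 3% (m = 50, s = 1) to 92% (m = 2, s = 1).

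The first range is narrow and the second is wide. On these assumptions the written limb is nearly always idle, but how many patients a different unit would affect is not known.

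**The case against.** The strongest reply is that a redundant condition does no harm. A confirmed 25% rise is a coherent rule that sites can apply, and redundancy suggests a slip in the unit without proving one. The working-group threshold is cited but not reproduced, so the documents alone cannot show which number or unit was intended. This stands, and it limits the remedy to reconciling the text.

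A reader might infer three stronger points that the documents do not support.

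- *Trivial PSA changes count as progression.* Not in general. A rise of at least 25% is still needed, it must be confirmed at least 3 weeks later, and early rises are set aside until week 12 apart from the stated exception. At 20 ng/mL the rule needs a rise of 5 ng/mL. Small absolute changes qualify only from a low reference value.
- *DCR and PFS are biased downward.* Not shown. DCR is built on CR, PR and SD under RECIST v1.1. PFS in Protocol Section 9.4.3.2 and SAP Section 6.7 counts clinical or radiologically documented progression or death, and its censoring table rests on RECIST assessments. Neither says whether PSA progression counts. Section 7.1 is also silent on PSA; the confirmation it describes is radiologic: "Disease progression should be confirmed per iRECIST 4 to 8 weeks after site-assessed first radiologic evidence of PD in clinically stable participants".
- *PSA alone decides progression in these patients.* Section 8.1.3 also requires a bone scan at baseline and bone-lesion evaluation every 9 weeks in all mCRPC patients, with a separate 2+2 progression rule. It allows multi-parametric MRI in bone-only disease.

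None of this makes the absolute limb work. The section sets two conditions, and at 0.08 ng/mL or above the second adds nothing to the first.

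**Conclusion.** The point holds as a defect in a stated threshold. In the unit written, the absolute limb is inactive at any baseline or nadir PSA of 0.08 ng/mL or more, and the rule is then a confirmed 25% rise. This follows from the stated numbers alone.

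That the limb is idle in nearly all patients is plausible, but it rests on an assumed PSA distribution. The size of any consequence depends on two things that the documents do not give: the intended threshold, and whether PSA progression enters DCR, PFS or the decision to stop treatment. The rule is written for mCRPC patients with non-measurable disease, and their share of Cohort D is not stated. The primary RECIST ORR, the 50% PSA response rule and the sample size do not depend on it. The correction is worth making because the text declares meeting the rule to be progression and the repair is cheap.

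**What to change.** In Protocol Section 8.1.3, reconcile the number and unit of the absolute limb with the working-group criteria that the section says it uses. State the threshold in one unit and require all local laboratory PSA results to be converted to that unit before the rule is applied. No value is proposed here, because the documents do not contain the source threshold.

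The cost is one sentence in the protocol, plus a reporting-unit entry in Appendix 2 or the data-entry instructions. The SAP has no PSA derivation to correct. If the sponsor intends PSA progression to be derived for analysis, the same value must go into a new SAP definition, which should say which endpoints it feeds. If not, the SAP needs no change on this point.

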## 8.2. Safety Assessments

Planned time points for all safety assessments are provided in the SoA (Section 1.3).

For each patient, ECGs, vital signs, laboratory tests, and other tests should be collected as shown in the SoA (Section 1.3).

Refer to Section 8.3 for details on the recording of AEs.

Lilly will periodically review evolving aggregate safety data within the study by appropriate methods.

### **8.2.1. Clinical Safety Laboratory Assessments**

- Lilly or its designee will provide the investigator with the results of safety laboratory tests analyzed by a central vendor, if a central vendor is used for the clinical trial.
- See Appendix 2 for the list of clinical laboratory tests to be performed and to the SoA (Section 1.3) for the timing and frequency.
- The investigator must review the laboratory report, document this review, and record any clinically relevant changes occurring during the study in the AE section of the case report form (CRF). The laboratory reports must be filed with the source documents. Clinically significant abnormal laboratory findings are those which are not associated with the underlying disease, unless judged by the investigator to be more severe than expected for the participant's condition.
- All laboratory tests with values considered clinically significantly abnormal during participation in the study or until the completion of Visit 803 should be repeated until the values return to normal or baseline or are no longer considered clinically significant by the investigator or medical monitor.
  - If such values do not return to normal/baseline within a period of time judged reasonable by the investigator, the etiology should be identified and the sponsor notified.
  - All protocol-required laboratory assessments, as defined in Appendix 2, must be conducted in accordance with the laboratory manual and the SoA (Section 1.3).
  - If there is an abnormal laboratory value or abnormal value for any other diagnostic or screening test (for example, blood pressure increased, neutrophils decreased, etc.) and it is known to be related to a disease diagnosis (for example, hypertension, neutropenia, etc.) this should be reported in the CRF as an AE. Do not enter the test abnormality, enter the disease diagnosis or categorical term. If laboratory values from non-protocol specified laboratory assessments performed at the institution's local laboratory require a change in participant management or are considered clinically significant by the investigator (e.g., SAE or AE or dose modification), then the event(s) must be reported in the CRF as AE(s).

#### **8.2.1.1. Hepatic Safety Monitoring**

##### **In study participants with baseline ALT/AST < 1.5× ULN**

If a study participant enrolled with baseline alanine aminotransferase (ALT)/aspartate aminotransferase (AST) < 1.5× ULN, experiences elevated ALT/AST ≥ 3× ULN, liver testing (Appendix 4) should be repeated within 2 to 5 days including ALT, AST, alkaline phosphatase

(ALP), total bilirubin (TBL), direct bilirubin, gamma-glutamyl transferase, and creatine kinase to confirm the abnormality and to determine if it is increasing or decreasing. If the abnormality persists or worsens, clinical and laboratory monitoring and evaluation for possible causes of abnormal liver tests, should be initiated by the investigator in consultation with the study medical monitor. Monitoring of ALT, AST, TBL, and ALP should continue until levels normalize or return to approximate baseline levels.

#### **In study participants with baseline ALT/AST $\geq 1.5 \times$ ULN**

If a study participant enrolled with baseline ALT/AST  $\geq 1.5 \times$  ULN, experiences elevated ALT/AST  $\geq 2 \times$  baseline, liver testing (Appendix 4) including ALT, AST, TBL, direct bilirubin, gamma-glutamyl transferase, and creatine kinase should be repeated within 3 to 5 days to confirm the abnormality and to determine if it is increasing or decreasing. If the abnormality persists or worsens, clinical and laboratory monitoring and evaluation for possible causes of abnormal liver tests, should be initiated by the investigator in consultation with the study CRP/CRS. Monitoring of ALT, AST, and TBL should continue until levels normalize or return to approximate baseline levels.

##### **8.2.1.1.1. Special Hepatic Safety Data Collection**

Additional safety data should be collected via the CRF/electronic data entry/designated data transmission methods if 1 or more of the following conditions occur:

#### **In participants enrolled with baseline ALT/AST $< 1.5 \times$ ULN:**

- Elevation of serum ALT/AST to  $\geq 5 \times$  ULN on 2 or more consecutive blood tests
- Elevated ALT/AST  $\geq 3 \times$  ULN and elevated TBL  $\geq 2 \times$  ULN

#### **In participants enrolled with baseline ALT/AST $\geq 1.5 \times$ ULN**

- Elevated ALT/AST  $\geq 3 \times$  baseline on 2 consecutive tests
- Elevated ALT/AST  $\geq 2 \times$  baseline and elevated TBL  $\geq 2 \times$  ULN

#### **In all study participants**

- Discontinuation from study treatment due to a hepatic event or abnormality of liver tests
- Occurrence of a hepatic event considered to be a SAE

##### **8.2.1.2. Allergic reaction and Hypersensitivity**

For suspected hypersensitivity reaction, laboratory tests may be obtained at the following time points:

- In the presence of generalized urticaria or if anaphylaxis is suspected.
- After the subject has been stabilized, obtain a sample within 1 to 2 hours of the event, however, samples may be obtained as late as 12 hours after the event as analytes can remain altered for an extended period of time. Record the time at which the sample was collected.

Obtain a follow-up sample at the next regularly scheduled visit or after 4 weeks, whichever is later.

All biologic agents carry the risk of systemic allergic/hypersensitivity reactions. Clinical manifestations of these reactions may include but are not limited to:

- Skin rash
- Pruritus (itching)
- Dyspnea
- Urticarial (hives)
- Angioedema (for example, swelling of the lips and/or tongue)
- Hypotension
- Anaphylactic reaction

Participants with clinical manifestations of systemic allergic/hypersensitivity reactions should be treated per local standard of care. Additional data describing each symptom should be provided to the sponsor in the CRF.

In case of anaphylaxis or generalized urticaria, additional blood samples should be collected as close as possible to the onset of the event (see Section 8.2.1 Clinical Safety Laboratory Assessments). Follow-up samples should be obtained at the next regularly scheduled visit or 4 weeks after the event, whichever is later. The lab results are provided to the sponsor via the central laboratory or via CRF.

### **8.3. Adverse Events and Serious Adverse Events**

Investigators are responsible for monitoring the safety of participants who have entered this study and for alerting Lilly or its designee to any event that seems unusual, even if this event may be considered an unanticipated benefit to the participant.

The investigator is responsible for the appropriate medical care of participants during the study.

Investigators must document their review of each laboratory safety report.

The investigator should provide AE verbatim terms and then the terms will be mapped by Lilly or its designee to corresponding terminology within the Medical Dictionary for Regulatory Activities (MedDRA) Lower Level Term (LLT) dictionary. The investigator will use Common Terminology Criteria for Adverse Events (CTCAE) version 5.0 to assign AE severity grades.

The investigator remains responsible for following, through an appropriate health care option, AEs that are serious or otherwise medically important, considered related to the investigational product or the study, or that caused the participant to discontinue the investigational product before completing the study. The participant should be followed until the event resolves, stabilizes with appropriate diagnostic evaluation, or is otherwise explained. The frequency of follow-up evaluations of the AE is left to the discretion of the investigator.

Lack of drug effect is not an AE in clinical studies, because the purpose of the clinical study is to establish treatment effect.

After the ICF is signed, study site personnel will record via CRF the occurrence and nature of each participant's preexisting conditions, including clinically significant signs and symptoms of the disease under treatment in the study. In addition, site personnel will record any change in the condition(s) and any new conditions as AEs. Investigators should record their assessment of the potential relatedness of each AE to protocol procedure, investigational product, via CRF.

The investigator will interpret and document whether or not an AE has a reasonable possibility of being related to study treatment, study device, or a study procedure, taking into account the disease, concomitant treatment or pathologies.

A “reasonable possibility” means that there is a cause and effect relationship between the investigational product, study device and/or study procedure and the AE.

The investigator answers yes/no when making this assessment.

Planned surgeries and nonsurgical interventions should not be reported as AEs unless the underlying medical condition has worsened during the course of the study.

If a participant’s investigational product is discontinued as a result of an AE, study site personnel must report this to Lilly or its designee via CRF, clarifying if possible, the circumstances leading to any dosage modifications, or discontinuations of treatment.

